8.2.2 Vital Signs and Weight

Vital signs were measured by a qualified staff member at all visits except Screening Visit 2. At each time point, the following vital signs were to be measured:

- Body temperature
- Pulse rate
- Respiratory rate
- Blood pressure (systolic and diastolic) after the subject rests (sitting or supine) for at least 5 minutes

Any measurement that was, in the opinion of the Investigator, abnormal AND clinically significant was considered as medical history if found prior to study medication injection or as an AE if found after study medication injection.

Weight measurements were to be taken at Screening Visit 1 and at Weeks 24, 52 (EOSa), 76, and 104 [Phase B End of Study (EOSb)] or ET.

8.2.3 Clinical Laboratory Evaluations

Fasting samples for clinical laboratory analysis were to be collected at Screening Visit 2 and Weeks 4, 12, 24, 36, 52 (EOSa), 64, 76, 88, and 104 (EOSb) or ET. At a minimum, the following tests were conducted:

- **Chemistry panel:** Albumin, alkaline phosphatase, alanine aminotransferase, aspartate aminotransferase, blood urea nitrogen, bicarbonate, calcium (corrected total), chloride, creatinine, glucose, lactate dehydrogenase, potassium, sodium, bilirubin (total)

- **Hematology:** Hemoglobin, hematocrit, red blood cell count, white blood cell count with differential, and platelet count
- **Urinalysis:** Clarity, specific gravity, pH, protein, glucose, ketones, nitrite, leukocytes, and occult blood

Urine microscopy was to be performed if urinalysis urine protein, leukocyte esterase, occult blood, or nitrite values were out of range, or if the Investigator deemed that the microscopy was clinically warranted

8.3 Bone Imaging Assessments

8.3.1 Knee BMD (qCT)

qCT scans of both knee joints were to be taken at Screening Visit 2 and at Weeks 12, 24, 36, 52 (EOSa), 64, 76, 88, and 104 (EOSb) or ET. The qCT scans assessed changes in BMD in both tibias across three compartments (medial, lateral, and total [medial + lateral]) and four volumes of interest (subchondral epiphysis, mid-epiphysis, juxtapophysis, and total).

For analysis, values of BMD that have undergone longitudinal correction will be used when available. Refer to Bioclinica's *Imaging Review Charter* for details on how corrections may have been made for scanner quality control.

8.3.2 Spine and Hip BMD (DXA)

Bone density DXA scans of the spine and hips were to be taken at Screening Visit 2 and at Weeks 24, 52 (EOSa), 76, and 104 (EOSb) or ET. Spine DXA scans assessed changes in BMD in two regions of interest: total (lumbar vertebrae L1 to L4) and adjusted total (L1 to L4 excluding any vertebral levels due to artifact). Hip DXA scans assessed changes in BMD in two regions of interest: total hip and femoral neck.

The DXA scanning assessed changes in the hips and spine and included the following parameters:

- **BMD:** individual subject's test, measured in g/cm²
- **T-score:** The number of standard deviations a subject's BMD differs from the mean BMD of a young, healthy sex-matched adult population
- **Z-score:** The number of standard deviations a subject's BMD differs from the mean BMD for an age-matched and sex-matched healthy population.

Negative T- and Z-scores indicate results below population mean, and positive scores indicate results above population mean. All T-scores were determined using reference data for Whites regardless of the individual subject's race. Z-scores were determined using African American reference data for Black or African American subjects. All other races or those with unknown race used the White reference data for Z-score calculations. Spine reference values were based on manufacturer's reference data; total hip reference values were based on NHANES-98 data.

For safety analysis, values of BMD and T-scores that have undergone longitudinal correction will be used when available. Refer to Bioclinica's *Imaging Review Charter* for details on how corrections may have been made for scanner quality control. Z-scores will not be summarized.

8.4 Efficacy Assessments

8.4.1 Pain NRS

The Pain NRS is an 11-point scale [0-10] for subject self-reporting of average knee pain in the previous 24 hours, where 0 represents no pain and 10 represents extreme pain. Subjects were prompted on their electronic device to report average pain daily (between 5:00 pm and 11:59 pm) in both knees at Screening Visit 2 and on the target knee only through the end of the study. An average weekly score (referred to as Pain NRS) will be calculated for each subject if they had provided a response for at least 4 out of 7 days in a given week. Weeks are defined as Day -7 through Day -1 (day before treatment) for baseline, Day 1 (day of treatment) through Day 7 for Week 1, Day 8 through Day 14 for Week 2, and so on as detailed in [Appendix 1](#). The day on which subjects completed their scheduled study visits (e.g. Week 4 Visit, Week 12 Visit, etc.) does not impact the above definition of weeks.

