6.1.5 DOSING AND ADMINISTRATION

SM04690 will be administered in the following dosage strengths:

- SM04690 0.07 mg in 2 mL Injectable Suspension
- SM04690 0 mg; 2 mL placebo (vehicle) injection only

The injectable investigational product or placebo is to be administered by the Unblinded Investigator as a single injection into the target knee joint once each at Day 1 and Week 24 (Phase A), and once each at Week 52 (EOSa) and Week 76 (Phase B). The Week 24, 52 (EOSa), and 76 injections may occur up to two weeks later than the Week 24, 52 (EOSa), and 76 visits, respectively, to allow for resolution of any intercurrent illness (e.g., infection) prior to the injection. The Unblinded Investigator must minimize any contact with the subject following the injections and may not perform any study assessments throughout the duration of the study. All subject contact for the remainder of the study is limited to the Blinded Investigator and other appropriate blinded study personnel.

Only 1 knee will be treated for each subject in this study. The injections can be done either through lateral or medial (including superior/suprapatellar, midpatellar and inferior/anterior) approaches, based on the standard practice of the Unblinded Investigator or the knee examination of the subject. Although not required, the injections may be guided by ultrasound or fluoroscopy without contrast if it is the standard practice of the Investigator.

Only topical anesthetics are allowed prior to study injection. Any local anesthetic injections are prohibited.

Prior to administration of the intra-articular knee injection, the subject should be blinded to observation of the study medication and injection procedure according to the processes specified in the Site-Specific Blinding Plan.

The Unblinded Investigator (injector) should place the needle into the joint and the total volume contained in the syringe is to be injected into the joint space. Because SM04690 drug product is a suspension, prior aspiration of synovial fluid into the syringe containing the injectate should be avoided to prevent trapping of particles within synovial aspirate/cellular content residues. If it is the standard practice of the injector to aspirate a small amount (0.3-0.5 mL) of joint fluid (if present) to confirm correct needle placement, this will have to be done with a separate empty

sterile syringe and, via syringe exchange, subsequently inject study medication using a new syringe.

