7.3.4 FINAL STUDY VISIT

Week 52 Phase A End of Study (EOSa)

This study visit should occur on Day 365 with a window of -3 to + 7 days. Subjects should fast for 8 hours prior to this visit.

The following procedures and assessments will be performed at Week 52 (EOSa):

- Collection of AE and concomitant procedures/therapies/medication data
- Review of medical history
- Vital signs measurements (pulse rate, blood pressure, respiratory rate, and temperature)
- Physical examination, including knee examination of both knees
- Weight measurement
- Venipuncture and collection of samples for clinical laboratory tests and biomarker analysis
- Radiograph – bilateral in weight-bearing fixed flexion position, posterior-anterior (PA) view X-ray
- qCT of both knees
- DXA of the spine and hips

For subjects who consent to participate in Phase B, prior to study medication injection, the Investigator should evaluate the subject for suitability to receive the injection (refer to [Section 6.1.9](#)). The injection may occur up to two weeks later than the Week 52 (EOSa) visit to allow for resolution of any intercurrent illness (e.g., infection) prior to the injection. The subject should complete all other Week 52 (EOSa) assessments and return for an unscheduled visit and injection in the case that they are not able to receive the injection at the Week 52 (EOSa) visit. If the subject is determined to be suitable for injection, the subject will receive an intra-articular study medication injection (or placebo).

Note: The Week 52 (EOSa) WOMAC and Patient Global Assessment must be completed prior to the Week 52 (EOSa) study medication injection

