3.2.7 Phase B Efficacy Endpoints

1. Characterization of change in OA pain in the target knee as measured by the weekly averages of daily pain NRS from baseline through Week 104 accounting for repeated injections
2. Characterization of change durability of treatment response in OA pain in the target knee as measured by the weekly averages of daily pain NRS through Week 104 elapsed from prior injection to repeat injection
3. Characterization of change in OA function in the target knee as measured by WOMAC Function from baseline through Week 104 accounting for repeated injections
4. Characterization of change durability of treatment response in OA function in the target knee as measured by WOMAC Function through Week 104 elapsed from prior injection to repeat injection
5. Characterization of change in mJSW as measured by radiograph of the target knee from baseline through Week 104 accounting for repeated injections
6. Characterization of change durability of treatment response in mJSW as measured by radiograph of the target knee through Week 104 elapsed from prior injection to repeat injection
7. Characterization of change in OA pain in the target knee as measured by WOMAC Pain from baseline through Week 104 accounting for repeated injections
8. Characterization of change durability of treatment response in OA pain in the target knee as measured by WOMAC Pain through Week 104 elapsed from prior injection to repeat injection
9. Characterization of change in OA disease activity as measured by Patient Global

Assessment from baseline through Week 104 accounting for repeated injections

10. Characterization of change durability of treatment response in OA disease activity as measured by Patient Global Assessment through Week 104 elapsed from prior injection to repeat injection

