8.4.2 WOMAC

The WOMAC is a widely used, proprietary outcome measurement tool used by health professionals to evaluate the condition of patients with OA of the knee and hip, including pain, stiffness, and physical functioning of a target joint. The WOMAC Version NRS 3.1 questionnaire were to be completed by the subject for their target knee in the evening (between 5:00 pm and 11:59 pm) remotely on their electronic device 5 days after Screening Visit 2 or up until the day before the Day 1 visit. After Day 1, monthly (every 4 weeks, with a window of \pm 3 days) WOMAC assessments were to be completed by the subjects for their target knee in the evening (between 5:00 pm and 11:59 pm) remotely on their electronic devices. At Weeks 24, 52 (EOSa), and 76, the WOMAC questionnaire must have been completed prior to the study medication injection; otherwise the results were not used in analysis. If an assessment was completed more than once within a window, only the first assessment will be used for analysis. All visit windows are detailed in [Appendix 1](#).

WOMAC consists of 24 questions in three domains: physical function (17 questions), pain (5 questions) and stiffness (2 questions). The response for each question in the NRS format ranges from 0 to 10. Each domain subscore as well as a total score are calculated by adding together the numerical responses for a range of 0 to 240 total points. For analysis, WOMAC scores will be linearly transformed to a 0-100 scale, where 0 represents no difficulty and 100 represents extreme difficulty.

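### Pain NRS windows: SAP Appendix 1 prints Week 6 as a 17-day window, and the Week 52 mean can include diary entries made after the Week 52 injection

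*SAP*

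**What the plan says.** SAP 8.4.1 counts Pain NRS weeks as "Day 1 (day of treatment) through Day 7 for Week 1, Day 8 through Day 14 for Week 2, and so on", refers to Appendix 1 for the full list, and adds that the day on which a scheduled visit takes place "does not impact the above definition of weeks". A weekly mean needs a response on "at least 4 out of 7 days in a given week". Appendix 1 then lists 104 weekly windows, with Week 6 given as Day 26 to 42 and Week 52 as Day 358 to 364.

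On timing, Protocol 7.3.4 says of Week 52: "This study visit should occur on Day 365 with a window of -3 to + 7 days". Subjects who continue into Phase B are injected at that visit, or later: "The injection may occur up to two weeks later than the Week 52 (EOSa) visit". Protocol 7.3.8 asks for a diary entry every evening from 5:00 pm, visit days included. It opens the Week 52 WOMAC and Patient Global window on Day 362.

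For those two questionnaires SAP 8.4.2 and 8.4.3 add a safeguard at Weeks 24, 52 and 76: they "must have been completed prior to the study medication injection; otherwise the results were not used in analysis". SAP 8.4.1 has no counterpart for Pain NRS. SAP Section 12 models Pain NRS as change from baseline by study week through Week 104, and it is the only efficacy outcome modelled there; the others are summarised descriptively.

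**The concern.** Appendix 1 is the table a programmer will code from, and its Week 6 row contradicts the rule in the text that refers to it. A 17-day window has no four-of-seven criterion: it is unclear whether 4 entries out of 17 would qualify. Coded literally, the same daily scores would also enter two weekly means. That adds correlation between Week 6 and Weeks 4 and 5 only, which the planned Toeplitz structure, with one correlation per lag, cannot represent. Week 6 lies in Phase A, but it still enters the baseline-to-Week-104 model.

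The Week 52 issue is one of consistency. The SAP treats a questionnaire completed after the Week 52 injection as unusable for Week 52, yet averages a diary score from the same evening into the Week 52 mean. For subjects seen early in the visit window, the last weekly mean of Phase A would then be partly a response to the first Phase B injection. The sentence in SAP 8.4.1 speaks of visit days. The consequence for injections is an inference, which holds because the injection is given at or after the visit.

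**Working it through.** **1. Weekly windows.** The rule in SAP 8.4.1 gives Week k = Day 7(k−1)+1 to Day 7k.

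- Week 5: 29 to 35, as printed. Week 52: 358 to 364, as printed. Week 104: 722 to 728, as printed.
- Week 6: 7×5+1 = 36, to 7×6 = 42. Printed: 26 to 42.
- Over all 104 rows, 103 match the rule; only Week 6 fails.
- Printed length: 42 − 26 + 1 = 17 days.
- Overlap: Days 26 to 28 are also in Week 4 (3 days) and Days 29 to 35 are also in Week 5 (7 days), so 10 days are shared.
- With Week 6 set to 36 to 42, all windows are contiguous, seven days long and free of overlap.

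**2. Week 52 mean.** Permitted visit days are 365 − 3 = 362 to 365 + 7 = 372. Assume a daytime injection at the visit on Day v, and count an entry that evening or later as post-injection. The number of such entries in Days 358 to 364 is 364 − v + 1.

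| Injection day | Entries after injection | Entries before injection | Post-injection share, full diary |
|---|---|---|---|
| 362 | 3 | 4 | 3/7 = 0.43 |
| 363 | 2 | 5 | 2/7 = 0.29 |
| 364 | 1 | 6 | 1/7 = 0.14 |
| 365 or later | 0 | 7 | 0 |

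The Day 362 row conflicts with another rule. The questionnaires must precede the injection, and their first permitted evening is Day 362. Usable questionnaire evenings for daytime injections on Days 362, 363, 364 and 365 are 0, 1, 2 and 3. The largest share that respects both rules is therefore 2/7.

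Two variations on these counts:

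- SAP 8.4.1 describes the score as average pain over the previous 24 hours, so the injection-day entry mostly describes time before a daytime injection. Leaving it out lowers the counts by one, to 2 of 7 (Day 362) and 1 of 7 (Day 363).
- With only the minimum of four entries, the shares could reach 3/4 = 0.75 (Day 362) or 2/4 = 0.50 (Day 363).

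If pain changes by d points on the post-injection evenings, the subject's Week 52 score moves by share × d. The documents give no value for d. For an illustrative d = 1 present from the first evening, the full-diary shift is 0.14 to 0.29, or 0.43 for a Day 362 injection, and it scales linearly with d.

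**3. Other injection weeks.**

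- Week 24, diary Days 162 to 168. The text of Protocol 7.3.3 allows visits from 169 − 3 = Day 166, so up to 3 entries (166, 167, 168) can follow an injection, or 2 if the questionnaires, whose window also opens on Day 166, came first. The schedule table in Protocol 7.3.7 allows only Day 169 to 172, which gives none.
- Week 76, diary Days 526 to 532. The earliest permitted visit is Day 533, so none.

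**The case against.** The Week 6 row is evidently a typing error: the text states the right rule and every other row follows it, so a careful programmer would use Day 36. That is fair, but SAP 8.4.1 sends the reader to the appendix for the detail, so it should not be left to the programmer's judgement.

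On Week 52, three objections carry weight. The 3-of-7 figure needs an injection that breaks the questionnaire-first requirement, so 2 of 7 is the better maximum. The windows are the same in both arms, there is no formal hypothesis test (Protocol 10.2), and the SAP describes Phase B as complementing the primary Phase A analysis. And the sponsor has been unblinded since the Phase A analysis (SAP 4.3), so changing a Week 52 derivation now could give values that differ from those already produced. All of this limits the weight of the point and shapes the fix. None of it explains why one patient-reported outcome has a pre-injection rule and another does not.

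A reader might also infer that Week 52 is the pre-injection reference for Phase B. SAP 8.1.1 says otherwise: Phase B keeps the Phase A baseline.

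A further inference would be that later weeks are mislabelled, since "The Week 24, 52 (EOSa), and 76 injections may occur up to two weeks later than the Week 24, 52 (EOSa), and 76 visits". A Day 372 visit with a two-week delay puts the injection on Day 386, so Weeks 53 to 55 (Days 365 to 385) would precede it. But SAP Section 12 labels and models these weeks by study week, which is what they are. SAP 3.2.7 does list durability endpoints through "Week 104 elapsed from prior injection to repeat injection", yet Section 12 specifies no durability or time-since-injection analysis that such weeks could distort. The general statement in SAP 5.2 that Phase B follows the Phase A approach does not supply one. The missing analysis is a separate question.

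**Conclusion.** Two faults stand.

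- **Week 6** is wrong as printed: 17 days instead of 7, with ten days shared with Weeks 4 and 5. This needs no assumption. Actual double counting occurs only if the row is programmed literally.
- **Week 52** can contain up to 2 of 7 post-injection entries in a full diary when the questionnaires came first, or 3 of 7 for a Day 362 injection. This assumes a daytime injection at the visit and counts the injection-evening entry as post-injection. It concerns only subjects injected on Days 362 to 364, and the documents do not say how many there were.

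The likely effect is some blurring of the Week 52 mean in both arms. Nothing in the documents points to a directional bias between treatments. Week 76 cannot be affected within its permitted window. Week 24 depends on which of two conflicting visit windows governs.

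**What to change.** 1. In SAP Appendix 1, correct Week 6 to Day 36 to 42. This costs nothing.
2. In SAP 8.4.1, exclude daily scores recorded on or after the actual Week 52 injection date from the Week 52 mean, and keep the four-entry minimum. A Day 362 injection still leaves Days 358 to 361, exactly four entries. The rule uses only the recorded injection date and does not depend on treatment.
3. Reconcile the Week 24 visit window in the text of Protocol 7.3.3 (±3 days) with the schedule table in Protocol 7.3.7 (+3 days). If the ±3-day text governs, apply the same exclusion to the Week 24 mean.
4. Record item 2 in SAP Section 15 as a change to the planned analysis, or run it as a sensitivity analysis beside the fixed-window result, because the sponsor is already unblinded to Phase A.
5. Reconcile the permitted Day 362 visit with the questionnaire window that opens that evening, and report how many subjects lost a Week 52 WOMAC for this reason. The SAP describes data collection in the past tense, so changing the e-diary setting would come too late for these data.

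The cost is SAP wording and a small change to the derivation code. A few subjects with sparse diaries may lose a Week 52 mean, and some Week 52 values may differ slightly from the Phase A analysis; both should be stated in the report. No change to injection timing is proposed.

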8.4.2 WOMAC

The WOMAC is a widely used, proprietary outcome measurement tool used by health professionals to evaluate the condition of patients with OA of the knee and hip, including pain, stiffness, and physical functioning of a target joint. The WOMAC Version NRS 3.1 questionnaire were to be completed by the subject for their target knee in the evening (between 5:00 pm and 11:59 pm) remotely on their electronic device 5 days after Screening Visit 2 or up until the day before the Day 1 visit. After Day 1, monthly (every 4 weeks, with a window of \pm 3 days) WOMAC assessments were to be completed by the subjects for their target knee in the evening (between 5:00 pm and 11:59 pm) remotely on their electronic devices. At Weeks 24, 52 (EOSa), and 76, the WOMAC questionnaire must have been completed prior to the study medication injection; otherwise the results were not used in analysis. If an assessment was completed more than once within a window, only the first assessment will be used for analysis. All visit windows are detailed in [Appendix 1](#).

WOMAC consists of 24 questions in three domains: physical function (17 questions), pain (5 questions) and stiffness (2 questions). The response for each question in the NRS format ranges from 0 to 10. Each domain subscore as well as a total score are calculated by adding together the numerical responses for a range of 0 to 240 total points. For analysis, WOMAC scores will be linearly transformed to a 0-100 scale, where 0 represents no difficulty and 100 represents extreme difficulty.

8.4.3 Patient Global Assessment of Disease Activity

The Patient Global Assessment is an 11-point [0-10] NRS on which the subjects rated how they felt their target knee OA was, considering all the ways in which their target knee OA may affect them. The NRS is anchored by descriptors at each end (“Very Good” on the left and “Very Bad” on the right). The Patient Global Assessments were to be completed by the subject in the evening (between 5:00 pm and 11:59 pm) remotely on their electronic device 5 days after their Screening Visit 2 or up until the day before the Day 1 visit. After Day 1, monthly (every 4 weeks, with a window of \pm 3 days) Patient Global Assessments were to be completed by the subjects in the evening (between 5:00 pm and 11:59 pm) remotely on their electronic devices. At Weeks 24, 52 (EOSa), and 76, the Patient Global Assessment must have been completed prior to the study

medication injection; otherwise the results were not used in analysis. If an assessment was completed more than once within a window, only the first assessment will be used for analysis. All visit windows are detailed in [Appendix 1](#).

For analysis, scores will be linearly transformed to a 0-100 scale, where 0 represents “Very Good” and 100 represents “Very Bad”. If an assessment was completed more than once within a window, only the first assessment will be used for analysis.

8.4.4 mJSW

Radiographs of the knee joints were to be taken at Screening Visit 1 and at Weeks 24, 52 (EOSa), 76, and 104 (EOSb) or ET. Bilateral radiographs were to be taken in a weight-bearing fixed flexion position, using a posterior-anterior view X-ray. All radiographs were submitted to an independent radiologist at the central imaging vendor who documented disease stage according to the Kellgren-Lawrence grading scale for compliance with inclusion/exclusion criteria, as well as mJSW for efficacy assessments. mJSW measurements will be reported to two decimal places.

